b) [name] MD – Roles for [name] include serving as primary research coordinator involved in data collection, subject recruitment, manuscript writing and preparation, data analysis, safety monitoring, and responding to adverse events and/or complications. She has completed all of her required CITI training to be IRB certified and has experience in clinical research. In addition she has been a resident physician in anesthesiology with the Icahn School of Medicine in good standing for the previous three years going on her fourth.

There are institutional processes to ensure that all persons assisting with the protocol will be well informed. The research personnel will conduct regular meetings and department email updates to review the results and safety data of the study. The research personnel will initiate the formation of a safety monitoring board for adverse effects, complications, or complaints from patient subjects.

5) Study Design

Prospective triple blinded randomized control trial. Recruitment will be done through a coordination of the operating schedule and the surgeon's office. Patients presenting for preoperative visits at the preoperative joint clinic will be approached. Patients routinely are seen by anesthesiologists at the pre operative testing clinic as part of pre operative anesthetic evaluation. Patients who meet the inclusion criteria will be approached by research personnel and details of the study will be explained. The consent will be obtained in the pre operative testing clinic after all questions are thoroughly answered. The team will finalize participation and ask the subject to sign study consent forms. All patients will be provided with copies of the IRB protocol and consent if they wish to have it. Copy of the consent form will be sent in a secured email to the potential subject. The email will be secured by entering in [SECURE] in the e-mail subject line. Once recruited blinding assessments will be done by the study team.

Patients will be assigned randomly using a computer- generated table of numbers to either IPACK block (IPACK group) or Periarticular infiltration (PAI group). Block team will perform all blocks. Resident anesthesiologist will know the group allocation but will not be involved in the study. Patients assigned to IPACK block group will receive 20cc 0.25% bupivacaine under USG guidance on the side of

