h) Data Management and Confidentiality

Data collected in excel file to be de-identified after initial collection. Excel file be subsequently encrypted and shared only between the above listed investigators via secure Mt. Sinai (chpnet) electronic mail. The information included in the data will be medical record number, age, gender, ASA class, type of surgery, pain score assessments, and time to first narcotic, total narcotic use and satisfaction/pain scores during the first 24 hours after surgery. Pain scores on arrival and discharge from PACU, PACU length of stay, location of pain, and ambulation distance with assistance on POD 1 as assessed by PT and activities of daily living (ADL's) on POD 1 as assessed by OT will be other data collected.

Only the research personnel will have access to the data. The data will be stored as a hard copy files and on a secure spreadsheet. The research personnel is responsible for the receipt of the data. The PI will keep the hard copies secure and any electronic data will be encrypted. No personal identifiers will be used. The data will undergo statistical analysis

 Mount Sinai	Protocol Name:	COMPARISON BETWEEN IPACK BLOCK AND PERIARTICULAR INFILTRATION IN TOTAL KNEE ARTHROPLASTY - A RANDOMISED CONTROLLED TRIAL
	Principal Investigator:	[name] [name].
	Primary Contact Name/Contact Info:	[name] MD. [REDACTED]
	Date Revised:	7/22/2017
	Study Number:	IF# 2087568 , GCO#17-04304

i) Provisions to Monitor the Data to Ensure the Safety of Subjects

Part I: Elements of Data and Safety Monitoring Plan

MSSM Principal Monitor:

Last Name: [name]

First Name: [name]

Academic Title: Attending Physician, Assistant Professor

Department: Anesthesiology

Mailing Address: Mount Sinai West [name]

[contact]

Fax:

E-mail: [contact]

MSSM Additional Monitor:

Last Name: [name]

First Name: [name]

Academic Title: Research Personnel, Physician

Department: Anesthesiology

Mailing Address: Mount Sinai West [name]

[contact]

Fax:

E-mail: [contact]

The principal monitor is a board certified anesthesiologist thus minimizing the risk to the subjects and further optimizing their health and wellbeing. Adverse events will be monitored as a standard of care everyone receives regardless of participation in the study. The safety and data information will be reviewed on a daily basis until the desired sample size is achieved. All temporary and/or permanent suspensions will be reported.

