[name] MD – Roles for [name] include serving as primary research coordinator involved in data collection, subject recruitment, manuscript writing and preparation, data analysis, safety monitoring, and responding to adverse events and/or complications. She has completed all of her required CITI training to be IRB certified and has experience in clinical research. In addition she has been a resident physician in anesthesiology with the Icahn School of Medicine in good standing for the previous three years going on her fourth.

 Mount Sinai	Protocol Name:	COMPARISON BETWEEN IPACK BLOCK AND PERIARTICULAR INFILTRATION IN TOTAL KNEE ARTHROPLASTY - A RANDOMISED CONTROLLED TRIAL
	Principal Investigator:	[name] [name].
	Primary Contact Name/Contact Info:	[name] MD. [REDACTED]
	Date Revised:	7/22/2017
	Study Number:	IF# 2087568 , GCO#17-04304

j) Withdrawal of Subjects

Patients may withdraw from the study at any given time by contacting any member of the research study group. Data will not be collected on patients who wish to withdraw. Patient do not need to withdraw consent in writing.

6) Risks to Subjects

If patients are injured or made sick from taking part in this research study, medical care will be provided. Generally, this care will be billed to the patient or their insurance in the ordinary manner and the patient will be responsible for all treatment costs not covered by insurance, including deductibles, co-payments and coinsurance. This does not prevent the patient from seeking payment for injury related to malpractice or negligence. Contact the investigator for more information.

As with any medication, there is a possibility of an allergic reaction. Although rare, possible complications include LA toxicity, hypersensitivity reaction, bleeding or local site infection, chance of pneumothorax. All anesthesiologists involved in patient care will be prepared for the prevention and rescue for any complications involving local anesthetic injections.

7) Provisions for Research Related Harm/Injury

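### The listed trial data contain no adverse-event or complication field, so the promised safety reviews have no specified study data and complications cannot be reported by arm from the planned data set

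*Combined protocol and SAP*

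**What the plan says.** Section 5h (Data Management and Confidentiality) gives the data list in three stretches. It opens with "The information included in the data will be medical record number, age, gender, ASA class, type of surgery, pain score assessments". It then adds time to first narcotic, "total narcotic use and satisfaction/pain scores during the first 24 hours after surgery". It ends with "Pain scores on arrival and discharge from PACU, PACU length of stay, location of pain, and ambulation distance with assistance on POD 1" and activities of daily living on that day. No adverse event, block complication or local-anaesthetic toxicity item is on the list.

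Section 1 (Objectives) and Section 5e (Endpoints) name no safety outcome. The analysis text under 5c provides chi-squared or Fisher's exact tests for dichotomous data but names no event to which they would apply.

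Section 5i says "Adverse events will be monitored as a standard of care everyone receives regardless of participation in the study" and, in the next sentence, "The safety and data information will be reviewed on a daily basis until the desired sample size is achieved". Section 4 makes two further commitments: "The research personnel will conduct regular meetings and department email updates to review the results and safety data of the study", and "The research personnel will initiate the formation of a safety monitoring board for adverse effects, complications, or complaints from patient subjects". Section 6 (Risks to Subjects), while describing complications as rare, says "possible complications include LA toxicity, hypersensitivity reaction, bleeding or local site infection, chance of pneumothorax".

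Two other provisions bear on the point. Under 5d, participation ends 24 hours after surgery. Under 5j, no data are collected on patients who wish to withdraw.

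**The concern.** The protocol commits to safety review in three places but does not say what the reviewers will review. The one explicit list of study data holds nothing on harms, and adverse events are assigned to routine care with no study definition, form, time window or breakdown by arm.

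This matters because the protocol presents IPACK as a novel technique that has not been compared with periarticular infiltration, and asks whether it gives superior analgesia. A result on opioid use should have the complication count in each arm beside it. Both arms also receive a bupivacaine adductor canal catheter, so local-anaesthetic toxicity is relevant in both. If only the 5h fields are collected, the final report can give no such count from its own data.

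**Working it through.** **1. Promises against data.** The point rests on text, so the first check sets the sections side by side.

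| Safety review promised | Safety data specified for it |
|---|---|
| Daily review (5i) | None; events left to standard care |
| Regular meetings on results and safety data (Section 4) | None |
| Safety monitoring board (Section 4) | None; no data flow or thresholds |

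Section 6 names five complications: local-anaesthetic toxicity, hypersensitivity, bleeding, local infection and pneumothorax. Of these, 0 of 5 appear in the 5h list. Safety outcomes in Section 1 and 5e: 0. Safety analyses in the analysis text: 0. No section says who records an event, on what form, over what period or by arm.

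**2. The plan's own figure.** The only derived number is the sample size in 5c: 2.58² × 0.5 × 0.5 / 0.1² = 166.41. This agrees with the stated 166, which is then raised to 200. The point does not depend on it, but 200 sets the scale below.

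**3. Scale, under assumptions.** The documents give no allocation ratio and no complication rates. I assume an equal split (200 / 2 = 100 per arm), no dropout, and a range of true rates p.

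Chance of at least one event in an arm = 1 − (1 − p)^100:

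| Assumed rate p | Chance of at least one event in 100 |
|---|---|
| 0.1% | 9.5% |
| 0.5% | 39% |
| 1% | 63% |
| 2% | 87% |
| 5% | 99% |

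**4. What a record could show.** With zero events in 100, the one-sided 95% upper bound is 1 − 0.05^(1/100) = 2.95%. The upper limit of the two-sided exact 95% interval is 1 − 0.025^(1/100) = 3.62%. For a comparison, power at a two-sided 0.05 level with 100 per arm is about 38% for 1% against 5%, and about 66% for 5% against 15%. Counts by arm would describe harms. They would not test them with useful power.

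**The case against.** The strongest reply is that 5h describes a spreadsheet for analysis, and nothing says it is the only input to safety review. Two physicians have safety-monitoring duties, 5i names two monitors, and a board is promised. All of them could act on what they see clinically. This stands. A reader might infer that no safety data would exist, or that nothing could ever prompt a suspension. The documents do not support that: the safety data are unspecified, not shown to be absent. But the reply identifies reviewers rather than data, so the gap in 5h remains.

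A reader might also infer that complications are likely to occur and go unrecorded. That depends on the assumed rate. Section 6 calls them rare, and at 0.1% or 0.5% an event in a given arm is less likely than not (9.5% and 39%).

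Nor do the documents establish that later chart retrieval would fail. Section 5h says the file is de-identified and carries no personal identifiers, yet it lists the medical record number and provides for hard copies. Retrieval is unclear rather than impossible, and in any case it is not planned.

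Finally, ambulation and activities of daily living on the first postoperative day may partly reflect a functional harm of a block. They are indirect measures and cover none of the Section 6 complications.

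**Conclusion.** The point holds in a limited form. The itemised data have no complication field, no safety outcome or analysis is planned, and three promised safety reviews have no specified study data. The Section 6 complications therefore cannot be reported by arm from the data set as planned. This finding comes directly from the text and needs no assumption.

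The figures in the working are illustrations only. They rest on equal allocation, 100 per arm with no dropout, and assumed event rates. They show that a record would be worth having for description, and that even zero events in an arm would leave rates up to about 3% possible.

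The gap does not affect the opioid comparison. It should be corrected because it changes what the trial can report about harms at little cost, and a complete record has to be in place before data collection starts.

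**What to change.** - **5h:** add, for each patient, a yes/no, time and severity entry for each Section 6 complication plus an entry for other events. Existing research staff complete it from randomisation to the end of the 24-hour participation period, using the same form in both arms. They should be masked where feasible; full masking cannot be assumed, since a chart may reveal which technique was used.
- **5i:** state that this record supplements standard-care monitoring and does not replace it, and that it is the listing sent to the daily review and to the board promised in Section 4.
- **Analysis text:** report counts by arm with exact confidence intervals, labelled descriptive.
- **Time window:** state that later events, such as an infection appearing after 24 hours, fall outside the record, so that a zero count is not over-read.
- **5j:** reconcile the record with the rule on withdrawal. At a minimum, keep events recorded before withdrawal and report the number of withdrawals by arm.

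The cost is an amendment to these sections, a few more columns, and slightly more data-abstraction time per patient. No study procedure is added.
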